14.2.5 Esophagoscopy

Esophagoscopies will be conducted at Screening in all subjects who have EC. Results of the most recent esophagoscopy that confirmed the diagnosis must be available for Screening. A repeat esophagoscopy is not required at Screening if the subject's signs and symptoms of EC have persisted since initial diagnosis. A repeat esophagoscopy is required at EOT for all subjects, if this complies with SOC. Additional esophagoscopies are recommended at the Day 42 and 6-Week FU visits only if symptoms have recurred and following local standard practices. Esophagoscopies should be performed at any unscheduled visits, if clinically indicated per local standard practices. Results from all esophagoscopies conducted during the subject's participation in the study should be included in the study database.

14.2.6 Spirometry

A spirometry test will be conducted at Screening or Baseline/Day 1 (prior to treatment) for all ABPA subjects. A repeat spirometry will be conducted at Day 42.

14.2.7 St. George's Respiratory Questionnaire (SGRQ)

For subjects with CPA, the latest available result on the St. George's Respiratory Questionnaire prior to Screening should be recorded on the eCRF as part of their medical history. Additionally, subjects with CPA will be administered the St. George's Respiratory Questionnaire at Screening or Baseline/Day 1 (prior to treatment), Day 90, Day 180, every 3 months while on therapy beyond Day 180, at EOT and at the 6-Week FU visits.

14.2.8 Six-Minute Walk Test and Medical Research Council (MRC) Dyspnea Scale

For CPA subjects, the latest available result on the Six-Minute Walk Test prior to Screening should be recorded on the eCRF as part of their medical history. Additionally, subjects with CPA will undergo a Six-Minute Walk Test at Screening or Baseline/Day 1 (prior to treatment), Day 90, and Day 180. Subject's disability will be graded using the MRC Dyspnea Scale at the same time points.

14.2.9 Recurrence

Recurrence will be assessed at the 25-Day FU visit (25 days after EOT, 32 days after first dose) for subjects with VVC and at the 6-Week FU (42 days after EOT) for all other subjects as a secondary efficacy endpoint. For CPA subjects, recurrence will also be assessed at Day 180.

14.2.10 Survival

Survival status (collected as ACM) will be recorded at Day 30 for IC/candidemia subjects and at Day 42 for all diseases. ACM will be also recorded at Day 84 for subjects with IPA, disseminated/invasive dimorphic fungi and other emerging fungi, and at Day 90, Day 120 and Day 180 for subjects with CPA and ABPA. Information on survival status on Days 42, 84, 90, 120 and 180 will be collected for all subjects, irrespective of when treatment was discontinued. If the subject has died, the date and cause of death along with the reporting of SAE details will be recorded on the eCRF.

14.2.11 Assessment of Efficacy

Efficacy procedures will depend on each fungal disease. Efficacy will be assessed primarily in terms of Global Response at TOC for VVC, CMC, CPA and ABPA, and at EOT for all other fungal diseases. Global Response at other time points and Clinical Response and Mycological Response will also be assessed as secondary endpoints. In addition, secondary efficacy assessments will include disease-specific endpoints for selected fungal diseases. See [Section 14.2](#) for detailed efficacy procedures and [Section 18.4.1](#) for a detailed discussion of efficacy assessments.

The following study procedures will be performed to assess treatment outcome for all subjects:

- Clinical signs and symptoms of fungal disease ([Section 14.2.1](#))
- Mycological testing (including, but not limited to, fungal cultures, T2 testing, KOH and other fungal stains) ([Section 14.2.2](#))
- Radiological assessments including esophagoscopy and other imaging scans, as applicable (e.g., X-ray, ultrasound, CT and MRI) ([Section 14.2.3](#) and [Section 14.2.5](#))
- Serological testing (including, but not limited to, GM, *Coccidioides* titers, or β -D glucan levels) ([Section 14.2.4](#))

Additional procedures (i.e., spirometry, SGRQ, 6-Minute Walk Test and MRC Dyspnea Scale) will be conducted for selected fungal diseases. See [Section 14.2.6](#), [Section 14.2.7](#) and [Section 14.2.8](#), respectively.

14.3 Safety Procedures

14.3.1 Vital Signs

Vital signs, including blood pressure (systolic and diastolic), heart rate, respiratory rate, weight and body temperature, will be measured at Screening, Baseline/Day 1, EOT and unscheduled visits as appropriate. For CPA subjects, weight will also be determined at the Day 180 visit.

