14.3.2 General Physical Examination

A general physical exam will be done at Screening and EOT. A general physical exam will also be conducted at the 6-Week FU for all subjects, except VVC subjects. The physical examination will include an abbreviated assessment of general appearance, skin, eyes, heart, chest and abdomen.

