14.3.3 Clinical Laboratory Safety Assessments

Clinical laboratory tests will include hematology, blood chemistry and urinalysis.

For all fungal diseases except VVC, samples for clinical laboratory tests will be collected at Screening, every 14 days up to EOT if clinically indicated, at EOT, at the 6-Week FU if clinically indicated, and at unscheduled visits if clinically indicated. If indicated, these may be done more frequently as follow-up to a laboratory abnormality.

In addition to the above, if still on treatment, CPA subjects will have blood drawn on Day 90 and Day 180 for albumin, platelet count, CRP and plasma viscosity assessment.

For VVC subjects, safety labs will be collected at Screening, [REDACTED] and 25-Day FU (32 days after first dose). Safety labs will be repeated at any unscheduled visit, if applicable.

The following laboratory parameters will be determined:

Hematology

▪ White blood cell (WBC) count ^a	▪ Hemoglobin
▪ Red blood cell (RBC) count	▪ Hematocrit
▪ Platelet count ^b	▪ C-reactive protein ^b
	▪ Plasma viscosity ^b

a: Differential WBC count will include percentages for segmented neutrophils, lymphocytes, monocytes, eosinophils and basophils, and absolute counts for neutrophils, lymphocytes, monocytes, eosinophils and basophils.

b: On Day 90 and Day 180 for CPA subjects only.

Blood Chemistry

▪ Sodium	▪ Glucose
▪ Potassium	▪ Albumin ^a
▪ Alkaline Phosphatase	▪ Aspartate aminotransferase (AST/SGOT)
▪ Chloride	▪ Alanine aminotransferase (ALT/SGPT)
▪ Blood urea nitrogen (BUN)	▪ Gamma glutamyl transferase (GGT)
▪ Creatinine	▪ Lactate dehydrogenase (LDH)
▪ Total creatine phosphokinase (CPK)	▪ Bilirubin (total, direct, and indirect)
▪ Total protein	▪ Prothrombin (PT) and international normalized ratio (INR)

a: On Day 90 and Day 180 for CPA subjects only if still on treatment.

Urinalysis

▪ Appearance (clarity, color)	▪ Glucose
▪ Specific gravity	▪ Ketones
▪ pH	▪ Protein
▪ Blood	▪ Leukocytes
▪ Bilirubin	▪ Urobilinogen

Reflex Microscopic Evaluation

▪ Bacteria	▪ Mucous
▪ Casts	▪ RBC
▪ Crystals	▪ WBC
▪ Epithelial cells	

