- l. For EC subjects only. A repeat esophagoscopy is required at EOT for all subjects, if allowable per SOC practice. Additional esophagoscopies are recommended at the Day 42 and 6-Week FU visits only if symptoms have recurred and following local standard practices. Esophagoscopies should be performed at any unscheduled visits, if clinically indicated per local standard practices.

PROCEDURE Visit	Screen ^a	BL/ D1 ^a	D2 (PK Only)	D3- D5	D7- D10	Study Day 14 and then Every 14 days during Tx	D42	D84 ^t	D90 ^u	D120	D180	EOT	Unsch. Visits	FU 1 ^b (6- WK)	FU 2- FU 3 ^b
Days (allowable window)	-1 (-3)	Prior to Tx		±2 d	±2 d	±2 d	±7 d	±7 d	±7 d	±14 d	±14 d	±3 d	AP	± 7d	AP

- m. For subjects who have EC, results of the most recent esophagoscopy that confirmed the diagnosis must be available for Screening. A repeat esophagoscopy is not required at Screening if the subject's signs and symptoms of EC have persisted since initial diagnosis.
- n. If clinically indicated.
- o. For IPA subjects, subjects with disseminated/invasive dimorphic fungi and subjects with other emerging fungi.
- p. At Day 180, weight will be determined for CPA subjects only. No other vital sign measurements will be collected for CPA or any other subjects.
- q. Sparse PK samples for Population PK analysis will be collected during the following time windows on Day 2 (anytime post dosing); between Days 3 to 5 (predose) and between Days 7 to 10 (predose). Additional blood PK samples will be collected when clinically indicated. The time of dosing and sample collection must be recorded on the subject diary and eCRF. In addition to blood samples, other fluid and tissue samples may be collected for ibrexafungerp PK determination when clinically indicated. Tissue samples collected as part of SOC procedures (e.g., biopsies) may be sent for drug concentration analysis, when available.
- r. Baseline radiological assessments for invasive fungal disease should be performed ideally within 72 hours of Screening. However, assessments performed up to 7 days before/after the first administration of study medication may be used to confirm the diagnosis of the fungal disease if none exists within the ideal window.
- s. Pregnancy tests may be conducted more often (e.g., on a monthly basis), per local regulations.
- t. For CMC D84 is TOC unless EOT occurs first
- u. For CPA and ABPA D90 is TOC unless EOT occurs first

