**Table 7      Disease-Specific Secondary Endpoints**

Disease-Specific Secondary Endpoints	
Acute Invasive candidiasis / Candidemia	

○ Completion of study drug antifungal treatment (i.e. no recurrence, no use of other antifungal treatment, no discontinuation for any reason)

	
Chronic Severe Mucocutaneous Candidiasis (CMC)	

○ Percentage subjects with mycological cure at Day 84

○ Percentage subjects with clinical response by Day 42 and Day 84

○ Percentage of subjects with continued symptom relief at 6-week FU

	
Chronic Pulmonary Aspergillosis (CPA) disease-specific endpoints	

○ Six-Minute Walk Test and MRC Dyspnea Score at Day 90 and Day 180

○ Weight change at Day 90 and Day 180

○ Improvement in inflammatory markers (CRP, plasma viscosity, albumin, platelet count, disease-specific immunoglobulin levels) at Day 90 and Day 180

○ Change in total IgG and Aspergillus IgG at Day 90 and Day 180, if elevated at Baseline

○ All-cause mortality at Day 90, Day 120 and Day 180

○ Recurrence at Day 180

	
Allergic Bronchopulmonary Aspergillosis (ABPA) disease-specific endpoints:	

○ Percentage of subjects who exhibit a Global Response at Day 42

○ Percentage of subjects with Clinical Improvement (as measured on a 4-point scale) at TOC, Day 90, Day 180, then every 3 months while on therapy, and 6-Month FU

○ Percent decline in total IgE (baseline IgE minus time point IgE/baseline IgE) at Day 42 and Day 90

○ Number of subjects who experience an ABPA exacerbation at the 3-Month and 6-Month FUs

○ Time to first ABPA exacerbation

○ Change in lung function (FEV1 and FVC) at Day 42

○ Number of Asthma exacerbations and ABPA exacerbations at the 3-Month and 6-Month FUs

○ All-cause mortality at Day 90, Day 120 and Day 180

	
Invasive Pulmonary Aspergillosis (IPA) disease-specific endpoint	

- The percentage of subjects who attain a GMI decrease including absolute and percent reduction from Baseline to Weeks 1, 2, 4 and 6, when feasible
- Time to achieve a clinically meaningful GMI absolute (<0.5) and percent (=>50%) decrease
- All-cause mortality at Day 84

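### CPA weight change at Day 90 is a listed secondary endpoint, but no Day 90 weight is scheduled

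*Protocol*

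**What the plan says.** **The endpoint.** SAP Table 7 gives the CPA endpoint as "Weight change at Day 90 and Day 180". The protocol synopsis and protocol Table 2 name the same two time points.

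**The measurement.** Protocol section 14.3.1 is the only text that schedules a weight: "Vital signs, including blood pressure (systolic and diastolic), heart rate, respiratory rate, weight and body temperature, will be measured at Screening, Baseline/Day 1, EOT", with unscheduled visits added as appropriate. It then makes one addition for this disease: "For CPA subjects, weight will also be determined at the Day 180 visit". Footnote p to protocol Table 14 says the same, "At Day 180, weight will be determined for CPA subjects only", and SAP Table 3 repeats that footnote.

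**The visit.** Day 90 is a real CPA visit. It is the TOC visit unless EOT comes first (protocol section 10.1; Table 14, footnote u), and several CPA assessments are already scheduled for it.

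**The concern.** An endpoint needs a measurement at its named time. Here one of the two named times has none. If sites follow the schedule, the Day 90 weight line in the report will either be empty or be filled from a subgroup selected by when it stopped treatment. Subjects who end treatment at about three months may differ in either direction from those who continue: some will have done well, others will have stopped for failure or intolerance. A summary labelled Day 90 would not show this to the reader. Weight matters in this disease, since protocol Table 5 lists weight loss among the signs of a suboptimal CPA response.

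**Working it through.** The plan gives no figure to reproduce. The check sets the endpoint against the schedule and then does arithmetic on the visit windows.

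**1. The vital signs row.** In protocol Table 14 and SAP Table 3, as read from the PDF, the row appears shifted by one column: the footnote p mark sits under EOT although its text concerns Day 180. Moving the marks back one column gives Day 180, EOT and unscheduled visits, which agrees with section 14.3.1. The Day 90 cell is blank with or without that correction, so the gap is not caused by the text extraction.

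**2. Other possible sources of a Day 90 weight.**
- The general physical examination takes place at Screening, EOT and the 6-Week FU, and its content omits weight: "The physical examination will include an abbreviated assessment of general appearance, skin, eyes, heart, chest and abdomen" (protocol section 14.3.2).
- A targeted examination is scheduled for CPA at Day 90 (protocol Table 9), but nothing says that it includes a measured weight.
- Protocol section 18.0 analyses data without imputation unless otherwise stated. SAP section 8.3 summarises vital signs at scheduled visits. Neither document gives a visit-mapping or carry-forward rule for weight.

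**3. Comparison with the other CPA measures.**

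| Measure | Scheduled at Day 90 | Scheduled at Day 180 | Source |
|---|---|---|---|
| Walk test and MRC scale | Yes | Yes | Protocol 14.2.8 |
| Inflammatory blood markers | Yes, if on treatment | Yes, if on treatment | Protocol 14.3.3 |
| Total and *Aspergillus* IgG | Yes | Yes | Protocol 14.2.4 |
| SGRQ | Yes | Yes | Protocol 14.2.7 |
| Weight | **No** | Yes | Protocol 14.3.1 |

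The wording for the others is explicit: "subjects with CPA will undergo a Six-Minute Walk Test at Screening or Baseline/Day 1 (prior to treatment), Day 90, and Day 180" and "CPA subjects will have blood drawn on Day 90 and Day 180 for albumin". Weight alone has the later visit without the earlier one, which looks like an omission.

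**4. Visit windows (protocol Table 14).**
- Day 90 ±7: 90 − 7 = 83 and 90 + 7 = 97, so Days 83 to 97.
- Day 180 ±14: 180 − 14 = 166 and 180 + 14 = 194, so Days 166 to 194. This does not overlap the Day 90 window.
- The only scheduled weight that can fall on Days 83 to 97 is therefore an EOT weight. With the EOT window of ±3 days around the last dose, that means a last dose between about 83 − 3 = Day 80 and 97 + 3 = Day 100.

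**5. What each group of CPA subjects contributes.** Treatment may run to 180 days or longer (protocol section 10.1).

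| Last dose | Scheduled weight in Days 83 to 97 |
|---|---|
| Before about Day 80 | None; the EOT weight falls earlier |
| About Day 80 to Day 100 | Possible, from the EOT visit |
| After about Day 100 | None; the TOC is the Day 90 visit and the next scheduled weight is at EOT or Day 180 |

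**The case against.** The strongest reply has four parts.

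- **Weights may exist anyway.** Vital signs may be taken at "EOT and unscheduled visits as appropriate", and a site could record a weight during the Day 90 targeted examination. A reader might infer that a Day 90 weight can exist only for subjects who stop then. The documents do not support that. What they support is that none is scheduled for the others. Chance weights do not make a planned endpoint, so the gap remains.
- **TOC is not the same as Day 90.** A reader might also infer that weight cannot be described for CPA subjects at TOC. That goes too far. TOC is EOT for anyone who stops before Day 90, and weight is scheduled at EOT. The gap concerns subjects whose TOC is the Day 90 visit.
- **The amount missing is unknown.** Neither the number of CPA subjects nor their treatment durations are given. Saying that all continuing subjects could lack the value restates the schedule and is not an estimate.
- **The stakes are limited.** This is one time point of one disease-specific secondary endpoint in a single-arm study described as exploratory. The definition of CPA Global Response does not call for a measured weight, and weight change at Day 180 is scheduled.

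All four points stand as limits on the size of the problem. None supplies the missing measurement.

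**Conclusion.** The endpoint and the schedule do not match, in the protocol and in the SAP alike. Followed as written, the plan leaves Day 90 weight change empty or resting mainly on subjects whose EOT falls on Days 83 to 97, plus any unscheduled weights. This assumes that sites keep to the scheduled procedures and the stated windows; late EOT visits would blur the Day 80 to Day 100 range without changing the conclusion. The proportion of CPA subjects affected cannot be calculated from the documents. The primary endpoint, the Day 180 weight change and the other CPA Day 90 measures are unaffected. The point is modest in weight but worth correcting, because the repair is small and the endpoint is named in three places.

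**What to change.** **If CPA subjects are still being followed:** add weight for CPA subjects at the existing Day 90 visit in protocol section 14.3.1, in Table 14 (including footnote p) and in SAP Table 3. The cost to the subject is one weighing at a visit that already takes place. The change needs a protocol amendment and matching schedule entries.

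**If data collection is over:** amend SAP Table 7 to limit the formal endpoint to Day 180. List any weights recorded within Day 90 ±7 descriptively, giving the number available and how many come from EOT visits. EOT should not replace Day 90 as a named time point, because the endpoint never included it and its timing differs between subjects. The cost is one SAP line and a short listing.

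The documents do not settle which case applies. SAP Final 1.1, dated April 2024, describes some survival data collection in the past tense, but says nothing specific about CPA visits.

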14.3.2 General Physical Examination

A general physical exam will be done at Screening and EOT. A general physical exam will also be conducted at the 6-Week FU for all subjects, except VVC subjects. The physical examination will include an abbreviated assessment of general appearance, skin, eyes, heart, chest and abdomen.

14.3.3 Clinical Laboratory Safety Assessments

Clinical laboratory tests will include hematology, blood chemistry and urinalysis.

For all fungal diseases except VVC, samples for clinical laboratory tests will be collected at Screening, every 14 days up to EOT if clinically indicated, at EOT, at the 6-Week FU if clinically indicated, and at unscheduled visits if clinically indicated. If indicated, these may be done more frequently as follow-up to a laboratory abnormality.

In addition to the above, if still on treatment, CPA subjects will have blood drawn on Day 90 and Day 180 for albumin, platelet count, CRP and plasma viscosity assessment.

For VVC subjects, safety labs will be collected at Screening, [REDACTED] and 25-Day FU (32 days after first dose). Safety labs will be repeated at any unscheduled visit, if applicable.

The following laboratory parameters will be determined:

Hematology

▪ White blood cell (WBC) count ^a	▪ Hemoglobin
▪ Red blood cell (RBC) count	▪ Hematocrit
▪ Platelet count ^b	▪ C-reactive protein ^b
	▪ Plasma viscosity ^b

a: Differential WBC count will include percentages for segmented neutrophils, lymphocytes, monocytes, eosinophils and basophils, and absolute counts for neutrophils, lymphocytes, monocytes, eosinophils and basophils.

b: On Day 90 and Day 180 for CPA subjects only.

Blood Chemistry

▪ Sodium	▪ Glucose
▪ Potassium	▪ Albumin ^a
▪ Alkaline Phosphatase	▪ Aspartate aminotransferase (AST/SGOT)
▪ Chloride	▪ Alanine aminotransferase (ALT/SGPT)
▪ Blood urea nitrogen (BUN)	▪ Gamma glutamyl transferase (GGT)
▪ Creatinine	▪ Lactate dehydrogenase (LDH)
▪ Total creatine phosphokinase (CPK)	▪ Bilirubin (total, direct, and indirect)
▪ Total protein	▪ Prothrombin (PT) and international normalized ratio (INR)

a: On Day 90 and Day 180 for CPA subjects only if still on treatment.

Urinalysis

▪ Appearance (clarity, color)	▪ Glucose
▪ Specific gravity	▪ Ketones
▪ pH	▪ Protein
▪ Blood	▪ Leukocytes
▪ Bilirubin	▪ Urobilinogen

Reflex Microscopic Evaluation

▪ Bacteria	▪ Mucous
▪ Casts	▪ RBC
▪ Crystals	▪ WBC
▪ Epithelial cells	

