### 3. General Statistical Considerations

Continuous data will be described using descriptive statistics (i.e. number of subjects, mean, standard deviation (SD), median, minimum, and maximum). Categorical data will be described using the subject count and percentage in each category. For the summary statistics of all numerical variables unless otherwise specified, minimum and maximum will be displayed to the same level of precision as reported. Mean and median will be displayed to one level of precision greater than the data collected. Standard deviation / standard error will be displayed to two levels of precision greater than the data collected. P-values will be rounded to three decimal places. If a p-value is less than 0.001 it will be reported as “<0.001.” If a p-value is greater than 0.999 it will be reported as “>0.999.” Data will be displayed in all listings sorted by disease category.

All analyses for ibrexafungerp will present the results by fungal disease, disease category ([Table 5](#)), and enrollment category. Overall response for global, clinical, and mycological responses will be presented for all disease categories combined.

Unless otherwise specified, baseline will be defined as the last non-missing assessment prior to or on the date (and time if appropriate) of the first dose of study drug. Change from baseline is defined as: post-baseline value – baseline value. For parameters measured over time, observed data and changes from baseline will be described for each time point.

The study day will be calculated as follows:

If the assessment date occurs on or after the date of the first dose of study drug:

Study day = assessment date – first dose date + 1.

If the date of interest occurs before the date of the first dose of study drug:

Study day = assessment date – first dose date

There is no study day 0.

All analyses will be conducted using SAS® Version 9.4 or higher. All statistical tests will be two-sided and interpreted at a 5% significance level.

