### **3.3 General Handling of Missing Data**

For incomplete dates related to concomitant medications, the dates will be imputed as follows:

If the incomplete date is a start/onset date:

- (1) if the month and year are present, then the first day of the month will be used for day.
- (2) if only the year is present, then the first day of January will be used for month and day.

If the incomplete date is an end date:

- (1) if the month and year are present, then the last day of the month will be used for day.
- (2) if only the year is present, then the last day of December will be used for month and day. If the reported year is the same as the informed consent year, then the informed consent date will be used.

Dates that are completely missing will not be imputed.

Baseline values that are missing will not be imputed. Subjects who have missing subgroup values will not be included in that particular subgroup analyses.

If efficacy data are missing and the subject has not been deemed a success or failure the outcome will be categorized as unknown.

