## **8.2 Clinical Laboratory Evaluations**

Summary tables will be presented for clinical laboratory test results (hematology, blood chemistry, and urinalysis) at collection visits for subjects in the safety population. For all fungal diseases except VVC, samples for clinical laboratory tests will be collected at Screening, every 14 days up to EOT if clinically indicated, at EOT, at the 6-Week FU if clinically indicated, and at unscheduled visits if clinically indicated. If indicated, these may be done more frequently as follow-up to a laboratory abnormality. In addition to the above, CPA subjects will have blood drawn on Day 90 and Day 180 for albumin, platelet count, CRP and plasma viscosity assessment. For VVC subjects, safety labs will be collected at Screening, [REDACTED] and 25-

Day FU (32 days after first dose). Safety labs will be repeated at any unscheduled visit, if applicable.

All relevant clinical laboratory tests in chemistry, hematology, and urinalysis will be classified as Low, Normal, and High according to the normal ranges. This categorical data will be summarized in shift tables comparing the extreme results at each visit with those at the baseline visit. Extreme post-baseline results will also be summarized as described in [Section 8.2.2](#). When there are multiple values within a visit for a particular laboratory variable, the worst value will be taken (worst being the smallest value for criteria below a certain threshold or the largest value for criteria above a certain threshold). If a subject has a value below the threshold and above the threshold, the value furthest from the threshold will be chosen.

In data listings, laboratory values will be compared to normal ranges; out-of-range and clinically significant laboratory values will be identified.

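### No pre-dose draw is explicitly scheduled for CRP or plasma viscosity in CPA subjects, so two of the five markers in the inflammatory-marker endpoint have no stated baseline

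*Protocol*

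**What the plan says.** The endpoint is in Protocol Table 2 and, in the same words, in SAP Table 7: "Improvement in inflammatory markers (CRP, plasma viscosity, albumin, platelet count, disease-specific immunoglobulin levels) at Day 90 and Day 180".

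The timing of the blood markers is set in Protocol 14.3.3:
- The hematology footnote (b) on platelet count, CRP and plasma viscosity reads "On Day 90 and Day 180 for CPA subjects only".
- The chemistry footnote (a) on albumin reads "On Day 90 and Day 180 for CPA subjects only if still on treatment".
- The body text, after an on-treatment condition, says "CPA subjects will have blood drawn on Day 90 and Day 180 for albumin, platelet count, CRP and plasma viscosity assessment".
- For all diseases except VVC, the same section also says "samples for clinical laboratory tests will be collected at Screening". It presents the CPA draw as an addition to that schedule.

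SAP 8.2 repeats the CPA sentence without the on-treatment condition: "In addition to the above, CPA subjects will have blood drawn on Day 90 and Day 180".

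Under SAP Section 3, "baseline will be defined as the last non-missing assessment prior to or on the date (and time if appropriate) of the first dose", and change is the post-baseline value minus the baseline value. SAP 3.3 adds: "Baseline values that are missing will not be imputed".

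**The concern.** Improvement needs a pre-treatment reference. CRP and plasma viscosity are not in most routine safety panels, so a site will order them when the protocol tells it to. The only days the protocol attaches to them fall after treatment has started. A site that follows the footnote has no reason to request either assay at Screening.

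A listed secondary endpoint would then have no change score for those two markers. There would be a temptation to report Day 90 and Day 180 levels, or the change between them, as if they showed improvement. In a single-arm study there is no control group against which to read a post-treatment level, so the pre-dose value is the only internal reference.

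The Day 90 and Day 180 draws have a wording problem of their own. The Protocol body text and footnote a limit them to subjects still taking study drug, while footnote b and SAP 8.2 do not. CPA subjects can stop before Day 90, since TOC is defined as EOT or Day 90, whichever is earlier. Whether those subjects are sampled therefore depends on which sentence is followed.

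**Working it through.** The plan gives no figure to reproduce and no formula applies. The check is whether each of the five components has a planned pre-dose value.

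| Component | Timing stated for the marker itself | Could the Screening panel supply a baseline? |
|---|---|---|
| CRP | Day 90, Day 180 (footnote b, body text, SAP 8.2) | Only if the footnote is read as adding days |
| Plasma viscosity | Same as CRP | Same as CRP |
| Platelet count | Same footnote b | Probably (step 3) |
| Albumin | Same days, with on-treatment condition (footnote a) | Probably (step 3) |
| Disease-specific immunoglobulins | Serology at Screening and Baseline/Day 1 as applicable, then Day 90 and Day 180 (Protocol 14.2.4) | Not needed; baseline is planned |

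1. **Schedule tables.** In Protocol Table 14 and SAP Table 3, the laboratory row is marked at Screening without qualification. The CPA tag (footnote e) appears on that row only at Day 90 and Day 180. The tables therefore do not add a CPA-specific assay at Screening. They also mark the Day 90 and Day 180 cells as done if clinically indicated, which does not match the unconditional sentence in SAP 8.2.

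2. **Comparison with other CPA measures.** The SGRQ (Protocol 14.2.7) and the walk test with the MRC scale (14.2.8) are each given an explicit time point at Screening or Baseline before treatment. The evaluation of IgG change depends on an elevated Baseline value (Table 13, footnote b). CRP and plasma viscosity have no comparable wording.

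3. **Platelet count and albumin.** If footnotes a and b were exclusive, no subject with any other disease would ever have a platelet count or albumin measured in a multi-disease safety panel. That is implausible, so these two are probably part of the Screening panel for everyone. CRP and plasma viscosity are different. It is quite plausible that they are meant for CPA subjects alone, so this argument does not establish a Screening draw for them.

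4. **Count by reading.**
 - Footnotes exclusive: 1 of 5 components has a baseline and 5 − 1 = 4 do not.
 - Footnotes exclusive for CRP and plasma viscosity, routine panel for platelets and albumin: 3 of 5 have a baseline and 5 − 3 = 2 do not.
 - Footnotes only add days to the Screening panel: 5 of 5 have a baseline.

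5. **SAP rules.** A Screening value would qualify as baseline under SAP Section 3. If none was taken, SAP 3.3 leaves it missing and the difference cannot be formed. A Day 90 to Day 180 difference is available on every reading, but it does not measure change from the pre-treatment state.

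**The case against.** The strongest reply is that the section schedules laboratory samples at Screening, introduces the CPA draw as additional, and lists CRP and plasma viscosity in the hematology panel. Platelets, CRP and plasma viscosity share one footnote, so if it merely adds days for platelets it should do the same for the other two. All four blood markers would then have a Screening value. This is a tenable reading, and it rules out saying that the values will certainly be missing. It does not settle the matter, because footnote b gives the only timing specific to these assays and a site could reasonably follow it. The two readings lead to different data.

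Three stronger inferences are tempting but not supported:
- *The whole endpoint cannot be computed.* Immunoglobulins have a planned baseline, and platelets and albumin probably have one. SAP Section 3 also describes observed values, so Day 90 and Day 180 levels would still be reported.
- *Every CPA subject lacks a baseline CRP and plasma viscosity.* The documents show what is scheduled, not what was drawn. Some sites may have taken the assays at Screening or hold local pre-dose results.
- *Subjects who stop treatment are excluded from the Day 90 and Day 180 draws.* The condition is absent from footnote b and SAP 8.2, so this is a mismatch and not a settled rule.

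It is also fair to say that the stakes are limited. The study describes itself as exploratory, and the CPA response definitions in Protocol Table 16 do not name these four markers.

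**Conclusion.** The point holds as a gap in the stated schedule. No pre-dose draw is explicitly scheduled for CRP or plasma viscosity in CPA subjects, and followed as written the endpoint has no baseline for these 2 of 5 components. The range across readings is 0 to 4 of 5, and 2 is the most plausible count for the reason in step 3. The size in subjects cannot be given, because the documents plan about 220 subjects without a split by disease.

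This rests on two assumptions. The first is that improvement means change from baseline as SAP Section 3 defines it; neither document defines it separately for these markers. The second is that sites order CRP and plasma viscosity only on the days named. The primary endpoint is untouched. The point is still worth acting on, because the wording decides whether part of a prespecified endpoint can be derived at all.

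**What to change.** 1. In Protocol 14.3.3, state that CRP, plasma viscosity, platelet count and albumin are measured for CPA subjects on the existing Screening/Baseline blood draw. Reword footnotes a and b so that Day 90 and Day 180 are additional draw days. Carry the change into Protocol Table 14, SAP Table 3 and SAP 8.2.
2. Reconcile the on-treatment condition in the Protocol body text and footnote a with footnote b and SAP 8.2, which omit it. Reconcile the clinically-indicated tag on the Day 90 and Day 180 cells at the same time.
3. If enrolment is over, change the SAP only. Limit change-from-baseline summaries for each marker to CPA subjects with a recorded pre-dose value, report that number, and label all other Day 90 and Day 180 values as observed levels, not improvement.

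The first option costs two extra assays, CRP and plasma viscosity, on a sample already being taken. The second is a wording correction. The third is a short SAP clarification and a count from data already held.
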